## **Cover Page for Statistical Analysis Plan**

Sponsor-Investigator:	[name]
NCT Number:	NCT03539081
Unique Protocol ID:	201605777
Official Title:	Investigating Mechanisms of Human Spinal Cord Stimulation for Purpose of Treating Restless Leg Syndrome
Date of Document:	10 May 2023

Throughout the study, continuous measures are reported via means and standard deviations. Changes in femoral and brachial artery blood flow during SCS will be examined using two-way repeated measures ANOVA. Missing values for blood flow and MSNA variables will be imputed via marginal sums of squares using a general linear model approach. All analysis will be performed using SigmaPlot version 13.0 (Systat Software, Inc.), and p-values less than 0.05 will be considered statistically significant for all analyses.

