Principal Investigator (PI): [name]

Co-Investigators: [name]

[name]

[name]

[name]

[name]

[name]

Title of Study: Investigating Mechanisms of Human Spinal Cord Stimulation for the Purpose of Treating Restless Leg syndrome

Study Center: University of Iowa

Estimated number of subjects: 50 adults between the ages of 18-80

I.	Introduction.....	3
II.	Background.....	4
III.	Statement of Compliance.....	6
IV.	IRB Oversight	7
V.	Location of Study Procedures.....	8
VI.	Main Hypothesis	9
VII.	Main Screening Criteria.....	10
VIII.	Recruitment procedures	11
IX.	Inclusion Criteria	12
X.	Exclusion Criteria	12
XI.	Study Procedures	13
XII.	Possible Risks of the Study.....	15
XIII.	Adverse Event Reporting:.....	16
XIV.	Data Management	18
XV.	Subject Safety	19
XVI.	References.....	20

I. Introduction

The overall goal of this proposed study is to evaluate the underlying mechanisms of neural control of blood flow in the lower extremities in humans with restless leg syndrome (RLS). At least 15% of the general public suffers from RLS and many more may go undiagnosed. This unfortunate disorder leads primarily to a disturbing sensation within the patient's lower extremities that requires movement for relief (1, 2). The central hypothesis of our study is that physiological changes in lower limb blood flow as a result of thoracolumbar epidural Spinal Cord Stimulation (SCS) lead to the relief of RLS.

Patients aged 18-85 years with (n=25) and without RLS (n=25) that have recently having undergone Spinal Cord Stimulation (SCS) implantation (thoracolumbar) for chronic pain will be recruited from the Departments of Anesthesia and Neurosurgery, University of Iowa Hospitals and Clinics. The rationale for studying both RLS patients and non-RLS patients with chronic back pain is to initially test the effectiveness of Spinal Cord Stimulation (SCS) on lower limb blood flow in the absence of symptoms of RLS. In the non-RLS patients, we could determine if SCS does in fact alter limb blood flow. We hypothesize that RLS patients have altered muscle sympathetic nerve activity (MSNA) and blood flow correlating to severity of RLS symptoms, which will then be modulated by Spinal Cord Stimulation (SCS), allowing for resolution of symptoms in RLS with MSNA-mediated improvements in leg blood flow. We also hypothesize that SCS in RLS patients will reduce 24-hour ambulatory blood pressure in parallel with reductions in MSNA.

II. Background

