All key personnel (all individuals responsible for the design and conduct of this study) have completed Human Subjects Protection and Good Clinical Practice training.

IV. IRB Oversight

Human Subjects Office / IRB
J. [name]
[name]
[name]
[name]
FWA#: FWA00003007
Voice: [contact]
[contact]
Email: [contact]

V. Location of Study Procedures

University of Iowa
[name]
[name]

VI. Main Hypothesis

We hypothesize that epidural SCS will reduce symptoms in patients with RLS, and that this reduction is due to decreases in MSNA and improvement in leg blood flow.

Aim 1: To determine the extent to which epidural SCS decreases MSNA and improves lower limb blood flow and arterial stiffness inpatients treated with thoracolumbar epidural SCS for chronic back pain.

Hypothesis 1a: Thoracolumbar epidural SCS will abolish MSNA as measured by peroneal nerve microneurography to the lower limbs in patients with chronic back pain.

Hypothesis 1b: Thoracolumbar epidural SCS will increase femoral artery blood flow as measured by Doppler ultrasound and calf blood flow as measured by venous occlusion plethysmography after SCS in patients with chronic back pain.

Hypothesis 1c: Thoracolumbar epidural SCS will decrease leg arterial stiffness as measured by femoral-dorsalis pedis pulse wave velocity after SCS in patients with chronic back pain.

Aim 2: To determine the extent to which epidural SCS decreases MSNA and improves leg blood flow and arterial stiffness and reduces symptoms in patients with RLS.

Hypothesis 2a: Thoracolumbar epidural SCS will increase femoral artery and calf blood flow and reduce leg arterial stiffness inpatients with RLS.

Hypothesis 2b: Thoracolumbar epidural SCS will improve severity of clinical symptoms in patients with RLS.

Aim 3: To determine the extent to which SCS decreases 24-hour ambulatory blood pressure.

Hypothesis 3: Thoracolumbar epidural SCS will decrease 24-hour ambulatory blood pressure to a greater extent in patients with RLS compared with patients without RLS.

VII. Main Screening Criteria

Patients aged 18-85 years with and without RLS that have recently having undergone Spinal Cord Stimulation (SCS)implantation (thoracolumbar) for chronic pain will be recruited from the Departments of Anesthesia and Neurosurgery, University of Iowa Hospitals and Clinics.

VIII. Recruitment procedures

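### The main hypothesis and H2b concern RLS symptoms but no symptom measure is scheduled, and H3's between-group blood pressure contrast has data but no named test

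*SAP*

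**What the plan says.** **Hypotheses (Protocol, Section VI).** The main hypothesis begins "We hypothesize that epidural SCS will reduce symptoms in patients with RLS" and attributes the relief to lower MSNA and better leg flow. H2b repeats the symptom claim. H1a to H1c cover MSNA, femoral and calf flow, and leg pulse wave velocity (PWV) in chronic back pain. Aim 2 and H2a cover the same outcomes in RLS. Aim 3 asks whether SCS lowers 24-hour blood pressure, and H3 says that the fall is larger with RLS than without. The Introduction adds that RLS patients have altered MSNA and "blood flow correlating to severity of RLS symptoms". It gives the reason for including non-RLS patients: it "is to initially test the effectiveness of Spinal Cord Stimulation (SCS) on lower limb blood flow in the absence of symptoms of RLS".

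**Measurements (Protocol, Section XI).** Calf plethysmography is scheduled at both visits and microneurography at Visit 2. Ambulatory pressure is worn for one day on and one day off stimulation. Doppler flow is permissive at both visits: a leg or an arm artery may be recorded. No RLS symptom scale or symptom test is listed. The diary is described as holding activity, sleep and SCS times.

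**Analysis (SAP, single paragraph).** The one named test is in the sentence "Changes in femoral and brachial artery blood flow during SCS will be examined using two-way repeated measures ANOVA". Apart from that sentence, it says that "continuous measures are reported via means and standard deviations", that "Missing values for blood flow and MSNA variables will be imputed via marginal sums of squares using a general linear model approach", and that "p-values less than 0.05 will be considered statistically significant for all analyses". It names no primary outcome and does not name the two ANOVA factors.

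**The concern.** If no symptom score is recorded, no later analysis can recover H2b, and the main hypothesis loses its outcome. The severity correlation expected in the Introduction is lost with it.

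H3 fails differently. The data are planned, and a subset is enrolled for ambulatory pressure only, but nothing in the SAP compares the on-off change between groups. Whoever analyses it must choose a test after the fact. One tempting choice, a separate p-value in each group, does not test a between-group difference.

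The one named test is also poorly aimed. Brachial flow is in no hypothesis. Femoral flow is in two, but the protocol does not require it to be recorded, and a subject without femoral recordings adds nothing to that contrast.

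**Working it through.** The documents contain no power calculation, so there is no stated figure to reproduce beyond 25 + 25 = 50.

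**1. Is a symptom measure scheduled?** I looked in Visit 1, Visit 2, the ambulatory cuff visit with its diary, and the voluntary third visit. None lists one. Section XIV mentions questionnaires only as a kind of paper record. Reference 3 is a validation paper for an RLS severity test, but no procedure uses that test.

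**2. Which comparisons have a test?** The middle column takes the SAP literally. The last column supposes that the imputation sentence implies a model for every flow and MSNA variable.

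| Source | Outcome | Recording | Test by name | Generous reading |
|---|---|---|---|---|
| H1a | MSNA, back pain | scheduled | no | yes |
| H1b | femoral flow, back pain | optional wording | yes | yes |
| H1b | calf flow, back pain | scheduled | no | yes |
| H1c | leg PWV, back pain | scheduled | no | no |
| Aim 2 | MSNA, RLS | scheduled | no | yes |
| H2a | femoral flow, RLS | optional wording | yes | yes |
| H2a | calf flow, RLS | scheduled | no | yes |
| H2a | leg stiffness, RLS | scheduled | no | no |
| H2b | symptoms, RLS | none | no | no |
| H3 | 24-hour BP, RLS v non-RLS | on day and off day | no | no |

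By name: 1 + 1 = 2 of 10. Generous: 2 femoral + 2 calf + 2 MSNA = 6 of 10. Without Aim 2 MSNA, which no lettered hypothesis states, it is 2 to 5 of 9. Four of the ten have no test on either reading.

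**3. Why H3 needs the interaction (illustration only).** Assume 25 per group, independent groups, the same true on-off change of d SD in both, and a two-sided paired t-test at 0.05 in each group (24 df, critical value 2.064, noncentrality d√25). Let p be the chance of a significant decrease in one group. The chance of a decrease that is significant in RLS but not in non-RLS is p(1 − p).

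| d (assumed) | d√25 | p | p(1 − p) |
|---|---|---|---|
| 0.2 | 1.0 | 0.159 | 0.134 |
| 0.4 | 2.0 | 0.484 | 0.250 |
| 0.6 | 3.0 | 0.821 | 0.147 |

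The interaction test errs in that direction 0.05/2 = 2.5% of the time. A simulation at d = 0.4 (200,000 runs) gave 0.249 for separate tests and 0.024 for the interaction.

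**4. What the H3 interaction test can detect.** It is a two-sample t-test on the on-off changes, 25 v 25 (48 df, noncentrality d√(25/2)). It reaches 80% power at d = 0.81 SD of the change. The normal approximation agrees: (1.960 + 0.842) × √(2/25) = 0.79.

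**The case against.** - **The two ANOVA factors could be SCS state and RLS group.** That is plausible, but the SAP does not say so. The sentence is confined to femoral and brachial flow, so it cannot reach blood pressure.
- **The count of ten depends on what is counted.** This stands. It leaves out Aim 3's overall blood pressure effect, the baseline RLS difference, the severity correlation and the mechanism claim. A reader might take 2 to 6 of 10 as the complete coverage; it is only a tally of the listed comparisons.
- **The illustration describes a procedure nobody proposed.** This also stands. A reader might infer that the plan carries a 13% to 25% false-finding rate, but no passage plans separate within-group blood pressure tests.
- **Multiplicity.** A reader might infer a family-wise error of up to 1 − 0.95^10 = 40%. The SAP does not name ten tests, so that figure is not a property of the plan. What the documents support is that a 0.05 threshold covers all analyses and no outcome is primary.
- **Optional flow may be loose, consent-style wording.** Possibly. H1b does specify femoral Doppler, and the third visit lets subjects complete missed items, but only if they wish. The optional wording touches only the two femoral comparisons; calf flow and MSNA are scheduled.
- **The laboratory contrast.** Because Section IX admits patients still planning implantation, a reader might infer a before-and-after-implantation design. Support is thin: Sections I and VII describe patients with an implant, and Section VIII speaks of those already implanted. What does stand is that the SAP refers to flow during stimulation and H1b to flow after it, and that on versus off is explicit only for ambulatory pressure.

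**Conclusion.** The point holds and needs correcting before the results are interpreted. As written, the study collects no data for H2b or for the symptom part of its main hypothesis, and it reports H3 only descriptively although on-day and off-day pressures are recorded. Leg PWV has no test on any reading, and calf flow and MSNA enter at most through the imputation sentence. These conclusions rest on the text alone.

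The error rates for H3 rest on assumed effect sizes, full groups of 25 and an analysis that the documents do not propose. They show why the interaction must be named, not what the plan will do. A reader might also infer that no symptom scores exist. The documents show only that none is scheduled, and they do not say whether collection is complete.

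**What to change.** 1. **Protocol, Section XI, for subjects not yet measured.** Schedule a named RLS severity scale for the RLS group in each SCS state studied. Make femoral Doppler a required recording and leave brachial flow optional. If collection is complete without symptom scores, report H2b as not assessed.
2. **SAP model.** Analyse femoral flow, calf flow, MSNA, leg PWV and one named 24-hour blood pressure measure with SCS state, RLS group and SCS × group. Use either a mixed model or the existing two-way repeated measures ANOVA with these factors named. If a mixed model is chosen, delete the marginal-sums-of-squares imputation sentence and amend the sentence that restricts all analysis to SigmaPlot, so that two missing-data methods do not stand side by side.
3. **SAP contrasts.** H3 is the SCS × group interaction for blood pressure, on day versus off day. Aim 3 is the overall SCS effect on blood pressure. Aim 2 is the SCS contrast in RLS patients. H2b is a paired comparison of symptom scores. State whether Aim 1 uses non-RLS patients only, as the Introduction's rationale suggests, or all chronic-pain patients.
4. **Remaining hypotheses.** Give the baseline group difference, the severity correlation and the mechanism claim an analysis each, or label them exploratory.
5. **SCS contrast.** Reconcile the SAP's timing with H1b's and state the laboratory contrast.
6. **Hierarchy.** Name one primary outcome and label the rest secondary or exploratory. If outcome data have been seen, label the added tests exploratory.

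**Cost.** A short questionnaire, some recording time, SAP rewording and possibly other software. The recording changes help only subjects not yet measured, and the SAP is dated May 2023. Naming the H3 test does not give it power: below about 0.81 SD of the change, a null result should not be read as no difference.
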